| 
7.
ERIC: Promote adaptability
                                                | 
It is important that BBTI is delivered with fidelity to maximize treatment effectiveness; however, adaptability is vital to ensure that treatment delivery meets the needs and preferences of the Veteran and clinician. BBTI was developed with a few core elements (e.g., four rules) yet delivery can be adapted (e.g., all in-person vs. combined in-person and telehealth) and therapeutic techniques integrated to meet the Veterans' needs (e.g., motivational interviewing, behavioral activation). BBTI is an adaptable treatment and this advantageous feature will be emphasized during BBTI training and highlighted at planned education efforts with local Primary Care teams.
                                                       |
| 
CFIR: Adaptability
                                                               | 
Example: PCMH clinicians, during the PCMH intake may identify insomnia with mild depression. Treatment planning, through shared decision making, may include initiation of BBTI plus behavioral activation to assist with staying out of bed during the day (stimulus control) and engaging in pleasant activities (a way to avoid naps).
                                                                                                                                                                                                                                                                                                                                                                                                   |
| 
8.
ERIC: Involve patients and family; Use their feedback; Prepare them to be
 | 
Behavioral interventions require active patient involvement to achieve optimal outcomes. As part of BBTI training, PCMH clinicians will be taught to encourage and reinforce Veterans to actively participate in care to maximize positive change. Also, PCMH clinicians will be encouraged to speak with Veterans about the referral and treatment process to identify ways to improve their care experience. Lastly, PCMH clinicians will be encouraged to discuss involving Veteran's family and/or support
                                                                                                                                                                                                                                     |

---

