During the implementation and post-implementation phases, site PIs and enrolled PCMHI clinicians will complete a quarterly survey (n≥12 surveys/site, n≥48 surveys across all sites) about strategies from the bundle proposed (e.g., “Did providers use X strategy to promote delivery of BBTI?”). These surveys will assess the uptake of strategies, longitudinally, across study phases. Site PIs and PCMHI clinicians will also be asked to rate each strategy on its importance during the last three months (i.e., how vital a strategy was to improving implementation) and its feasibility during that time (i.e., how possible a strategy was to implement). The surveys will be managed through Microsoft Forms by the study coordinator at the coordinating site .

Each enrolled site PI and PCMHI clinicians will also be asked to complete a demographics form through Microsoft Forms after verbal consent.

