**Analyses.** The interviews will be semi-structured with broad, open-ended questions to assess general impressions without leading the PIs or PCMH clinicians toward specific CFIR factors or implementation strategies. Interviews will be transcribed verbatim and coded by two independent staff in an inductive fashion to identify specific CFIR factors and other factors related to implementation of BBTI in PCMH. The initial codebook will be developed by trained qualitative staff followed by a group consensus review involving the PI and experienced implementation and qualitative Co-Investigators, Drs. [name] and [name]; this method was used by the PI in his pilot work and CDA. Discrepancies will be discussed until consensus is reached. After coding is complete, the identified CFIR factors will be aggregated and summarized using memos, and rated on their valence (positive [+1,+2] or negative [-1,-2] influence on implementation) and strength (strong [+1,+2] or weak [-1,-2] influence on implementation). Valence is determined by the influence the coded data has on the implementation process (i.e., factors that facilitate/hinder implementation) and strength by factors like level of participant agreement, strength of language, and concrete examples. Similar to initial coding, qualitative staff will complete CFIR ratings with discrepancies discussed as a group until consensus is reached.

Results of these quarterly surveys will be used as a preliminary descriptive analysis of the most/least commonly utilized strategies as well as the overall number of strategies utilized by each site. We will also evaluate the strategies by quadrant, the combination of rated importance and feasibility, which will help to provide context as to why a strategy may or may not have been utilized and how it may impact RE-AIM outcomes. Quadrant categories are: high importance/high feasibility (quadrant 1), low importance/high feasibility (quadrant 2), low importance/low feasibility (quadrant 3), and high importance/low feasibility (quadrant 4). Identifying the strategies utilized most frequently during the implementation and post-implementation period and those strategies rated as highly important and/or highly feasible will help inform future implementation efforts and which strategies to emphasize.

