| 
Facilitation
           A process of interactive problem solving and support that occurs in a context of a recognized need for improvement and a supportive interpersonal relationship.
 
Example: The Pittsburgh Implementation Team works with PCMH clinicians to enhance the delivery of BBTI, through the identification of barriers and facilitators at each site and supporting the implementation of strategies.
                                                                                                                                             |                                                                      |
| 
Increase demand
           Attempt to influence the market to increase demand for BBTI.
 
Example: Brochures about BBTI in PCMH are strategically placed in primary care waiting rooms, encouraging Veterans to talk with their PCPs about sleep problems.
                                                                                                                                                                                                                                                                                                          |                                                                      |
| 
Obtain and/or use patients/consumers and family feedback
           Develop strategies to increase patient/consumer and family feedback on the implementation effort.
 
Example: Veterans who initiate BBTI are asked to provide feedback about their experience and/or sent a survey on their experience.
                                                                                                                                                                                                                                                          |                                                                      |

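### The quarterly strategy survey has no item for bundle strategy 7 (adaptability) or for the family-involvement part of strategy 8, so the Aim 2 survey analysis cannot cover the whole bundle

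*Combined protocol and SAP*

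**What the plan says.** Section 5.5, Specific Aim 2, has site PIs and enrolled clinicians complete a "quarterly survey (n≥12 surveys/site, n≥48 surveys across all sites) about strategies from the bundle proposed" during the implementation and post-implementation phases. Respondents are also "asked to rate each strategy on its importance during the last three months", and on its feasibility over the same period.

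Section 5.6, Specific Aim 2, uses the results for a preliminary descriptive analysis of the "most/least commonly utilized strategies as well as the overall number of strategies utilized by each site". It also sorts strategies into four quadrants by importance and feasibility, and uses these results to inform which strategies to emphasize in future work.

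Table 3 in Section 5.1 sets out the bundle. Strategy 7 is "Promote adaptability". Strategy 8 opens "Involve patients and family; Use their feedback; Prepare them to be" and goes on to active participation in care. The form itself is Appendix 10.6.

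**The concern.** Aim 2 asks which strategies in the bundle help. A strategy with no row on the form cannot be reported as used or unused, cannot be rated and cannot be placed in a quadrant. It also cannot add to a site's count. Its absence from a list of most-used strategies would then reflect the form rather than the site.

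Each form asks only about the preceding three months, so quarterly ratings not collected at the time cannot be rebuilt later in the same form.

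**Working it through.** **The plan's survey count.** The survey runs through a 12-month implementation phase and a 6-month post-implementation phase (Section 5.1) at quarterly intervals: (12 + 6) / 3 = 6 rounds. This agrees with the form, which is numbered 1 to 6. With two respondents per site, 6 × 2 = 12 per site and 12 × 4 = 48 in all, which are the stated minimums. A site PI plus two clinicians would give 6 × 3 = 18 and 18 × 4 = 72, which also meets them. The count is not in dispute; the content is.

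**Matching Table 3 to the form.** Strategies 1, 3, 4, 5, 6 and 7 have one named component each. Strategies 2 and 8 have three each. That gives 6 + 3 + 3 = 12 components. The match is by strategy name.

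| Table 3 strategy | Components | Rows in Appendix 10.6 |
|---|---|---|
| 1 Blueprint | 1 | 1 |
| 2 Educational meetings; develop materials; distribute materials | 3 | 3 |
| 3 Implementation meetings | 1 | 1 |
| 4 Audit and feedback | 1 | 1 |
| 5 Facilitation | 1 | 1 |
| 6 Increase demand | 1 | 1 |
| 7 Adaptability | 1 | **0** |
| 8 Involve patients and family; use feedback; prepare for active role | 3 | **2** (feedback; active role) |
| Total | 12 | 10 |

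Six of the eight strategies are fully covered, one in part (8) and one not at all (7). The other 18 − 10 = 8 rows concern strategies not named in Table 3: quality monitoring, champions, formal commitments, ongoing training, academic partnerships, reminders, needs assessment and small tests of change.

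**What is missing from strategy 8.** Table 3 says "clinicians will be encouraged to discuss involving Veteran's family and/or support" system in the Veteran's care, and its example is a spouse attending a session. The feedback row asks about patient and family feedback on the implementation effort. The active-participation row concerns patients. The educational-meetings row lists family among the stakeholders who may be taught about BBTI. None asks about family taking part in care.

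**Could a row have dropped out of the copy?** This is unlikely. The bundle rows follow the order of Table 3. The row defined as "Attempt to influence the market to increase demand for BBTI" (strategy 6) is followed directly, in the same table, by the feedback row (part of strategy 8). Strategy 7 would fall exactly there.

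**After the fix.** Two added rows give 12 of 12 components, 8 of 8 strategies and 18 + 2 = 20 items. The minimums of 12 and 48 surveys do not change.

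**The case against.** The strongest case on the other side is that adaptability is measured elsewhere.

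- Section 5.6 plans to extract delivery mode and other adaptations, such as behavioral activation, from progress notes. These are the kinds of behavior that Table 3 gives for strategy 7.
- Interview guide 1 asks whether BBTI is adaptable. Guide 2 asks about fit, about the strategies used most and least (with named prompts allowed), and about what changed.
- CFIR factors identified in the interviews are rated for valence and strength, and Table 3 pairs strategy 7 with the CFIR factor of adaptability.

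All of this stands. A reader might infer that Aim 2 will learn nothing about adaptability, or that nothing can be recovered later; the documents do not support either. What these sources do not give is a quarterly record of whether a site promoted adaptability as a strategy, or how important and feasible that was.

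It can also be said that strategy 7 is delivered mainly through training, which every site receives, and so is not an optional site activity. But Table 3 also places the preparation of Veterans for an active role within training, and that has a row. Nor does site-specific choice of strategies explain the gap, because the form asks for ratings whether or not the clinic used the strategy.

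Three further readings go too far:

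- **That the survey ignores family.** It does not; only family participation in care is missing.
- **That the eight rows outside Table 3 are an error.** Section 5.1 expects sites to use other strategies, Section 5.6 plans an overall count, and the rows can be separated at analysis.
- **That Table 3 ranks strategy 7 above the others because it stresses the importance of adaptability.** That sentence is about fitting BBTI delivery to the Veteran and clinician; it does not rank the strategies.

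**Conclusion.** The point holds for the survey. As written, the form gives no use, importance or feasibility data on one of eight bundle strategies in any of its six rounds, and only partial data on another (two of three components). The most/least-used list, the per-site count and the quadrants in Section 5.6 inherit that gap.

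The consequence is limited. The survey is one of two Aim 2 sources and its analysis is descriptive. A reader might infer damage to the trial's main result, but neither Reach nor its power calculation draws on the survey.

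The conclusion assumes that Appendix 10.6 is the form in use and that Table 3 defines the bundle to which Section 5.5 refers. The documents give no reason for leaving the two components out.

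**What to change.** Add two rows to Appendix 10.6 in the existing format (definition, example, use, importance, feasibility): one for promoting adaptability, with an example such as all-telehealth delivery or BBTI combined with behavioral activation, and one for involving patients and family members in care. In Section 5.6, report the number of Table 3 strategies used per site alongside the planned overall count.

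The cost is two more rows on a Microsoft Forms survey, a protocol amendment and a slightly longer form each quarter.

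Timing matters because sites start six months apart, which is 6 / 3 = 2 rounds. The documents do not say whether any rounds have been collected. If the rows are added before the second site enters its implementation phase, at most two of site 1's six rounds lack them and the other sites are complete. A later change leaves more gaps. In either case the new items should be reported as not asked in the earlier rounds, not counted as strategies not used.

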## 5.6 Data Analysis

Specific Aim 1: To test the impact of BBTI+IS to improve RE-AIM outcomes and the sustainable delivery of BBTI without implementation support.

**Analyses.** Power estimates were based on Reach and were conducted for an incomplete stepped-wedge design with four steps (four participating sites) with site randomization every six months. An incomplete design was used since the implementation phase stops after 12-months rather than continuing until study completion. Using VA 2018 data from Primary Care and PCMHI dashboards as estimates, all Primary Care patients at the four sites, n=99,572, are considered the potential sample (denominator). The pre-implementation phase sample are Veterans seen for same-day PCMHI care across the four sites, n=4,778 (numerator). Considering the prevalence of insomnia is estimated as 44% of Primary Care patients, n=43,812, and there is minimal insomnia care being conducted in PCMHI currently, we expect to increase overall PCMHI care even if only a fraction of Veterans with insomnia can be reached through the implementation intervention (BBTI+IS). If 0.75% of the estimated 44% with insomnia are seen in PCMHI (n=329, n≈82/site, 1-2 new Veterans per week/site) we have 90% power to detect a significant increase of 6.88% in PCMHI care (4,778 to 5,107) from pre- to implementation phase. See Table 5 for power estimates at different levels of Reach.

Table 5. Power estimates for Reach.

|                          | % of unique Primary Care patients with insomnia (n=43,812) |        |        |        |        |        |          |
|--------------------------|------------------------------------------------------------|--------|--------|--------|--------|--------|----------|
|                          | 2%                                                         | 1.5%   | 1.25%  | 1%     | 0.75%  | 0.5%   | Baseline |
| New PCMHI patients       | 876                                                        | 657    | 548    | 438    | 329    | 219    | --       |
| Current same-day access  | 5,654                                                      | 5,435  | 5,326  | 5,216  | 5,107  | 4,997  | 4,778    |
| Current PC patients      | 99,572                                                     | 99,572 | 99,572 | 99,572 | 99,572 | 99,572 | 99,572   |
| Same day/PC patients (%) | 5.69                                                       | 5.46   | 5.35   | 5.24   | 5.13   | 5.02   | 4.80     |
| Power (%)                | 100                                                        | 100    | 99.96  | 99.02  | 90.03  | 59.25  | --       |

Descriptive statistics will be used to characterize the participating sites, PCMHI clinicians who are trained in BBTI (enrolled and not enrolled), and Veterans who received insomnia-related care in Primary Care/PCMHI (e.g., BBTI, CBT-I). Key enrolled clinician variables (self-report) will include socio-demographics, training, and work experience (e.g., degree, prior insomnia experience, duration working in PCMHI). For Veterans, variables of interest, from CPRS/CDW, include socio-demographics, vitals, service connection, combat history, and medical and psychiatric disorders, prescription medications, healthcare utilization, and information from progress notes (e.g., ISI scores). For Reach, Adoption, Implementation, and Maintenance outcomes, generalized linear mixed models will be used to compare the impact of the implementation strategy bundle across the three study phases for each site. These models will include a fixed main effect for study phase (pre, implementation, post) and random effects for clinician (nesting of Veterans within clinicians) and site (nesting of Veterans and clinicians within site); the primary comparison will be pre-implementation vs. implementation, with the secondary comparison implementation vs. post-implementation and long-term sustainability. Also, a we will conduct a comparison of outcomes from the study phases vs. a historical period prior to the study (1/1/20 – 12/31/20). While we did not power the study to assess interactions, to the extent possible, a fixed effect for site and the interaction between site and phase, will be introduced to assess differences between sites at the same study phase and differences between sites for the primary and secondary comparisons (e.g., differences from pre-implementation to implementation and from implementation to post-implementation, site 2 vs. site 3).

For treatment Effectiveness, using an intent-to-treat approach, we will fit a linear mixed model that tests for BBTI effectiveness (reduction of ISI score over the course of treatment) that includes a main effect of time (evaluation to last treatment session) and includes random effects for Veteran (multiple measurements per Veteran during treatment), clinician (nesting of Veterans within clinicians) and site (nesting of Veterans and clinicians within site). We will also attempt to control for clinician experience on treatment outcomes as well as mode of delivery of BBTI (e.g., in-person, phone, video) and other adaptations, such as integrating other

therapeutic techniques as indicated per the progress notes and extracted as part of the data query process (e.g., behavioral activation, motivational interviewing). Rates of response and remission from treatment will be calculated as will treatment effect sizes.

Specific Aim 2: To identify specific strategies that help promote the implementation of BBTI in PCMH using qualitative interviews and utilization surveys.

**Analyses.** The interviews will be semi-structured with broad, open-ended questions to assess general impressions without leading the PIs or PCMH clinicians toward specific CFIR factors or implementation strategies. Interviews will be transcribed verbatim and coded by two independent staff in an inductive fashion to identify specific CFIR factors and other factors related to implementation of BBTI in PCMH. The initial codebook will be developed by trained qualitative staff followed by a group consensus review involving the PI and experienced implementation and qualitative Co-Investigators, Drs. [name] and [name]; this method was used by the PI in his pilot work and CDA. Discrepancies will be discussed until consensus is reached. After coding is complete, the identified CFIR factors will be aggregated and summarized using memos, and rated on their valence (positive [+1,+2] or negative [-1,-2] influence on implementation) and strength (strong [+1,+2] or weak [-1,-2] influence on implementation). Valence is determined by the influence the coded data has on the implementation process (i.e., factors that facilitate/hinder implementation) and strength by factors like level of participant agreement, strength of language, and concrete examples. Similar to initial coding, qualitative staff will complete CFIR ratings with discrepancies discussed as a group until consensus is reached.

Results of these quarterly surveys will be used as a preliminary descriptive analysis of the most/least commonly utilized strategies as well as the overall number of strategies utilized by each site. We will also evaluate the strategies by quadrant, the combination of rated importance and feasibility, which will help to provide context as to why a strategy may or may not have been utilized and how it may impact RE-AIM outcomes. Quadrant categories are: high importance/high feasibility (quadrant 1), low importance/high feasibility (quadrant 2), low importance/low feasibility (quadrant 3), and high importance/low feasibility (quadrant 4). Identifying the strategies utilized most frequently during the implementation and post-implementation period and those strategies rated as highly important and/or highly feasible will help inform future implementation efforts and which strategies to emphasize.

Quantitative analyses will be led by [name] (Co-I/statistician) and qualitative analyses will be led by [name] (Co-I). Both will be completed in collaboration with study PI and other Co-Investigators/Consultants. Analyses are planned to be completed at the hub site, VAPHS.

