## 5.2 Recruitment Methods

Site PIs will invite (e.g., in-person, email, service line notification, phone) local PCMH clinicians to participate in BBTI training. PCMH clinicians who agree to attend training, upon completion will be invited to participate in the study. The goal is to recruit at least 2 PCMH clinicians from each site. See Appendix 10.1 for phone and email recruitment scripts. PCMH clinicians at local sites may also become aware of the opportunity to participate through participating colleagues and/or through the BBTI training available through TMS. They may then contact their local Site PI/coordinator or coordinating study PI/coordinator to express interest in participating.

Veterans will not be recruited. Retrospective data collection from Veterans' electronic health records (e.g., CPRS, CDW) will be used to obtain variables of interest related to Veteran treatment outcomes and variables related to PCMH clinician delivery of BBTI (or CBT-I). Our goal is to obtain retrospective data from at least n=329 Veterans, which would represent approximately 0.75% of unique Primary Care patients with insomnia across all four participating sites; this would result in 90% power for the Reach variable in RE-AIM (see Table 5 for full power analysis [section 5.6]).

There will be no participant payments.

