similar phases and across sites for similar phase comparisons. It will also allow for within site comparisons to evaluate the impact from pre- to implementation, from implementation to post-implementation, as well as the evaluation of long-term sustainability (>6-months post-implementation). SQL Server queries will be utilized to automatically update the data reported in the study's Microsoft Access database. The Access database front-end will be comprised of a form with buttons for on-demand updates to results from the existing queries (e.g., ISI scores from progress notes). Also, we will closely monitor the ongoing electronic health record update to Cerner. While the Cerner integration is not expected to impact this study, if participating sites do integrate Cerner during the study period, we will adapt our automated data query methods or utilize a standardized chart review form to collect data from individual Veteran records.

Reach, the primary outcome, will calculate the number of Veterans in PCMH who receive insomnia-related care. This may include (1) Veterans in Primary Care/PCMH clinics who receive an insomnia diagnostic code and/or a sedative hypnotic medication (see Table 4); (2) Veterans in Primary Care/PCMH clinics who initiate BBTI or CBT-I (indicated by a relevant progress note/encounter); (3) the proportion of Veterans in Primary Care/PCMH clinics who initiate BBTI/CBT-I relative to the Veterans in Primary Care/PCMH clinics who are eligible to initiate BBTI/CBT-I. Data collection will begin 1/1/2020 in order to compare to data during the study period (beginning 1/1/2021) and evaluate change. While the focus is on BBTI, initiation and engagement in CBT-I is also relevant as it will be important to evaluate different insomnia services delivered in Primary Care/PCMH (e.g., diagnoses, medications, BBTI, CBT-I).

Tracking these insomnia-related variables will allow us to measure trends in treatment initiation, diagnosis, and prescribing practices at different stages of the study (and prior to the study). However, this will still likely represent an underestimate of potential Reach since there will be Veterans with insomnia who turn down a PCMH visit, do not receive an insomnia diagnosis, and decline a sedative-hypnotic.

Table 4. Insomnia diagnoses and prescription sedative-hypnotics eligible for Reach denominator.

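### The 90% power attributed to Reach is power for same-day PCMHI care; no Reach measure has a stated baseline or power

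*Combined protocol and SAP*

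**What the plan says.** Section 5.6 opens its power paragraph with "Power estimates were based on Reach", for an incomplete stepped wedge with four sites and a step every six months. Table 5 is titled as power for Reach. Section 5.2 adds "Our goal is to obtain retrospective data from at least n=329 Veterans" and says of that number that "this would result in 90% power for the Reach variable in RE-AIM".

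The quantity behind these statements is a ratio. Its denominator is all 99,572 Primary Care patients at the four sites. Its starting numerator is the 4,778 Veterans seen for same-day PCMHI care. The result reads "we have 90% power to detect a significant increase of 6.88% in PCMHI care (4,778 to 5,107) from pre- to implementation phase". The rationale is that "there is minimal insomnia care being conducted in PCMHI currently", so that "we expect to increase overall PCMHI care even if only a fraction of Veterans with insomnia can be reached".

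Section 5.5 defines the outcome differently: "Reach, the primary outcome, will calculate the number of Veterans in PCMH who receive insomnia-related care". It lists three possible measures:

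1. an insomnia code and/or a sedative-hypnotic;
2. initiation of BBTI or CBT-I;
3. initiation as a proportion of eligible Veterans.

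Table 4 ties the Reach denominator to diagnoses and prescriptions.

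**The concern.** The power statement and the outcome definition describe different quantities. Same-day PCMHI care over all Primary Care patients matches none of the three measures in Section 5.5, and the analysis in Section 5.6 is planned for Reach, not for same-day care. Power for a change in a proportion or count depends on the baseline as well as on the increment. The plan prints no baseline for codes, prescriptions, initiations or eligible Veterans, so the 90% cannot be carried over to any of them.

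A reader of Section 5.2 in particular would take 90% as the power for the primary outcome. The same sentence presents 329 as a number of Veterans to collect data on, whereas in Table 5 it is the number of new patients above the pre-implementation level.

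**Working it through.** **Where 329 comes from (Section 5.6, Table 5).** 0.44 × 99,572 = 43,812. Then 0.0075 × 43,812 = 329 and 4,778 + 329 = 5,107, so the ratio moves from 4.80% to 5.13%. Spread over a year, 329/(4 × 52) = 1.6 per site per week, which agrees with the plan's 1-2. So 329 is an increment on 4,778, not a sample.

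**Reproducing the printed power.** Alpha, ICC, cell size and formula are not stated. I assume two-sided 0.05 and power = Φ(Δ/SE − 1.96), with Δ = 329/99,572 = 0.003304.

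- (a) Two unclustered samples of 99,572. Mean proportion 0.04964; SE = √(2 × 0.04964 × 0.95036/99,572) = 0.000973; ratio 3.394; Φ(1.434) = 92.4%.
- (b) Unclustered counts, variance from the higher count. 329/√(2 × 5,107) = 3.255; Φ(1.295) = 90.2%.
- (c) Stepped wedge with a random site effect and no period effect. The comparison is then almost wholly within site, so SE² ≈ p(1 − p)/(mK), with K = Σ ab/(a + b). Here a and b are a site's pre and implementation half-years, and m = 99,572/8 = 12,446 patients per site-half-year (assumed). Take five half-years with the first all control, so (a, b) = (1,2), (2,2), (3,2), (4,1). K = 0.667 + 1 + 1.2 + 0.8 = 3.667; SE = √(0.04717/(12,446 × 3.667)) = 0.001017; ratio 3.250; Φ(1.290) = 90.15%. The full model with ICC 0.001 gives 90.2%.

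| Increment | 219 | 329 | 438 | 548 |
|---|---|---|---|---|
| Printed (%) | 59.25 | 90.03 | 99.02 | 99.96 |
| (a) | 62.2 | 92.4 | 99.4 | 99.99 |
| (b) | 59.1 | 90.2 | 99.0 | 99.96 |
| (c), ICC 0.001 | 58.6 | 90.2 | 99.1 | 99.97 |

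Both an unclustered form and a site-effect form come within a point of Table 5. All of them use the same-day PCMHI rates.

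**The Section 5.1 layout.** Fit (c) gives every site a control period and stops after site 4's first implementation half-year. In Section 5.1, site 1 goes straight into implementation, the others wait 6, 12 and 18 months, and all get 12 months: (0,2), (1,2), (2,2), (3,2). K = 0 + 0.667 + 1 + 1.2 = 2.867; SE = 0.001150; ratio 2.874; Φ(0.914) = 82.0% (82.2% with ICC 0.001). With m doubled, SE = 0.000813; ratio 4.064; Φ(2.104) = 98.2% (98.3% with ICC 0.001). The unstated cell size alone puts the figure on either side of 90%.

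**Moving +329 onto a Reach baseline.** The denominator stays at 99,572, and both baselines are assumptions.

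- Baseline 1,000. (a) SE = 0.000482, ratio 6.86. (b) 329/√(2 × 1,329) = 6.38. Both give power above 99.99%.
- Baseline 10%, or 9,957. (a) SE = 0.001354, ratio 2.440, Φ(0.480) = 68.4%. (b) 329/√(2 × 10,286) = 2.294, Φ(0.334) = 63.1%.

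**The case against.** The best defence is that the proxy logic is on the page. The 329 are insomnia patients newly seen in PCMHI, added to existing volume because little insomnia care happens there now. The increment is therefore Reach-like and only the background count is not. Section 5.6 and the rows of Table 5 also name same-day PCMHI care openly, and Section 5.2 sends the reader to that table. All of this stands, and it makes the label less misleading in Section 5.6 than in Section 5.2. It does not close the gap: the plan never calls same-day care a proxy, never lists it under Reach and does not plan to analyse it as Reach.

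Two stronger readings are tempting, and the documents support neither.

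- A reader might infer from fit (b) that clustering was left out. Section 5.6 says that a stepped-wedge calculation was done, and a model with a site effect fits Table 5 about as well. Nothing can be concluded either way.
- A reader might infer that the trial is underpowered for Reach. The 63-68% requires +329 to be placed on the code-or-medication measure at a baseline that I assumed, and the plan gives no source for +329 there. For initiation, starting from the low level that the plan describes, the same arithmetic gives power near 100%.

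**Conclusion.** The mismatch holds and needs no calculation: the 90% belongs to same-day PCMHI care, and Reach as defined in Section 5.5 has neither a baseline nor a power figure. The size and direction of the consequence are not established. On assumed baselines and a two-sided 0.05, power for +329 runs from about 63-68% (10% baseline) to near 100% (1,000 or fewer).

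A secondary point is that the printed power cannot be tied to the Section 5.1 layout without the missing inputs. One site-effect model gives about 82% or about 98% there, depending only on whether a site-half-year holds 12,446 patients or twice that. These figures assume equal sites, no period effect and an ICC of 0.001. They omit the clinician effects in the Section 5.6 model and are not estimates of the trial's power.

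**What to change.** Preferred: name the Section 5.5 measure that is powered. State its baseline and the year it comes from, together with alpha, ICC, cell size and formula. Then restate the power for the Section 5.1 layout, in which site 1 has no pre phase, and for the Section 5.6 model with site and clinician effects. The data already planned from 1 January 2020 could supply the baseline.

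Failing that, relabel the 90% wherever it is attributed to Reach (Section 5.2, the Section 5.6 text and the Table 5 title) as power for same-day PCMHI care, and say plainly that Reach has no stated power.

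In either case, reword Section 5.2 so that 329 is the number of new Veterans above the pre-implementation level, not a sample size.

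The cost is a choice of measure, one recalculation and a few text edits; the fallback needs only the edits but leaves the primary outcome without a power figure. Sites, schedule and sample stay as they are. The downside is that the restated power may be less favourable than 90%.
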